3.4.2 In-depth interviews, focus group discussions and surveys with health care workers

Interviewees (health providers) will be selected through a mix of purposive and random sampling. Based on the data collected through the medAL-monitor tool, we will select health facilities based on relevant criteria such as levels of uptake of and compliance with the algorithm. Within the health facilities, providers will be randomly selected among those available on that day.

Interviews will be conducted using a semi-structured interview guide developed for the study. The questionnaire will cover several themes, such as 1) experience using the ePOCT+ tool, 2) management of tablets in the facility, 3) training on the content and use of the algorithm, 4) experience with the e-learning modules and the supervision and mentorship tool (medAL-monitor).

For each question, probes will be used to generate further explanations from study participants. Each interview will be conducted as an informal discussion with open questions, leaving room for the HCW to express additional elements. In order to reduce study bias, participants will be strongly encouraged to be as open as possible in expressing their opinion and reassured on full confidentiality. The tools for the interviews and focus groups can be found in **Appendix 2**.

To complement the qualitative data, we will quantitatively evaluate the impact of using the ePOCT+ tool and the additional training and mentorship provided through the project on clinicians' competencies and confidence in their skills and decisions in Phase 1. The initial 3-day training will be implemented with a pre- and post- test administered to the participants. The e-learning platform will also come with short tests at the end of each module for the learners to self-assess their

understanding of the content. Lastly, baseline and end-line assessments and surveys will be used to compare intervention and control facilities. Similar assessment tools will be used in Phase 2, except a control group will not be available for comparing the difference in clinical competencies between baseline and end-line.

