10.2 Estimated number of beneficiaries

In Phase 1, the number of direct beneficiaries include children in the intervention arm of the study (n=17,100) and HCWs using ePOCT+ (n=75) for a total of 17,175 people. Indirect beneficiaries may include caregivers and immediate family members who are less exposed to infectious diseases as a result of better cure rates of their child/sibling. Using an average rural household size of 5 people according to the 2004-2005 Demographic and Health Survey, the number of expected indirect beneficiaries is approximately 68,400 (i.e. 4*17,100, excluding the sick child who is a direct beneficiary).

In Phase 2, we expect that an average of 200 children per month per HF will be managed using ePOCT+, which corresponds to around 500,000 consultations over 2 years in the 100 HFs. The number of direct beneficiaries will be less than this, because children may come to the facility more than once, either for the same illness or a different illness over the 2-year study period. In Phase 2,

approximately 300 HCWs are expected to directly benefit from using ePOCT+ and their clinical decision support and e-learning functions. Additionally, approximately 20 users of medAL-monitor and 30 users of medAL-outbreak at the district and national levels will also benefit directly. Lastly, all individuals who are capacitated IT systems management, ML, adaptation of the algorithm through MedAL-Creator, etc. will be included as direct beneficiaries (n=50). Because of high coverage of the intervention in phase 2, indirect beneficiaries will be the entire population of the intervention districts (n=1,053,000) as a result of 1) less exposure to infectious diseases due to better cure rates of sick children; 2) reduced drug pressure and likelihood of antibiotic resistance due to reduced antibiotic prescriptions; and 3) reduced risk of illness due to more effective outbreak detection and response.

10.3 Statistical analyses for the primary outcome measures in the cluster randomized controlled study of Phase 1

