10.5 Analyses of data from operational research studies

Quantitative data from cross-sectional quality of care surveys, provider clinical competency or knowledge assessments, and caregiver and patient interviews will be analyzed using conventional statistical methods to compare means (t-tests or paired t-tests) or frequencies (chi-square tests) across intervention groups or time periods. Regression analysis may also be used to explore associations of multiple predictors with outcomes of interest.

All interviews and focus-group discussions will be audio-recorded with the participant's informed consent. Detailed notes will be taken during the interviews. Records will be manually transcribed in its original language (Kiswahili) and translated into English. A qualitative data analysis software (e.g. Nvivo) will be used to code the English interview transcripts in order to identify emerging themes. A predefined list of codes based on the interview guide and the recurrent themes highlighted in the detailed notes will be used. New codes will be created when new themes are identified during more detailed analysis of the transcripts. Deductive coding will be used to extract the themes based on the interview guide, but inductive coding will also be used to extract any unexpected themes that arise during the interviews.

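### Healthcare worker competency and confidence are assessed at baseline and end-line in both Phase 1 arms, but no baseline-adjusted, cluster-aware comparison between arms is specified.

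*Protocol*

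**What the plan says.** Protocol 3.4.2 adds a quantitative evaluation to the qualitative work. It covers clinicians' "competencies and confidence in their skills and decisions in Phase 1", and states that "baseline and end-line assessments and surveys will be used to compare intervention and control facilities". For Phase 2 it plans similar tools, "except a control group will not be available for comparing the difference in clinical competencies between baseline and end-line". The arm comparison over time therefore exists only in Phase 1, and the baseline is planned in both arms.

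Protocol 10.5 gives the analysis. It states that "provider clinical competency or knowledge assessments, and caregiver and patient interviews will be analyzed using conventional statistical methods", which it describes as methods to "compare means (t-tests or paired t-tests) or frequencies (chi-square tests) across intervention groups or time periods". It adds: "Regression analysis may also be used to explore associations of multiple predictors with outcomes of interest". Confidence scores are not named separately in 10.5.

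Protocol 3.1 randomises facilities, 20 per arm, by region and facility type. The adjustment for clustering and stratification factors appears in Protocol 10.3, whose heading limits it to the primary outcome measures of Phase 1. The SAP supplied covers the later medAL-mentor study and does not analyse healthcare worker competency or confidence.

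**The concern.** Of the tests named in 10.5 for a mean score, a two-sample t-test on end-line scores makes no use of the baseline, and a paired t-test compares time points rather than arms. Regression is permitted but is not tied to the arm comparison or to the baseline score. The trial would collect a useful covariate in both arms without committing to use it.

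The same sentence treats healthcare workers as independent, although facilities are the randomised unit. If scores within a facility are correlated, a plain t-test understates the standard error.

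At stake are the precision and validity of the competency and confidence comparison, and the freedom to choose among several analyses once the data are seen.

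**Working it through.** **Inputs from the documents.** There are 20 facilities per arm (Protocol 3.1). Protocol 10.2 expects 75 healthcare workers using ePOCT+ in Phase 1; this is a count of beneficiaries and not an assessment sample. No sample size, standard deviation, target difference, power or baseline to end-line correlation is given for these assessments, so there is no planned figure to reproduce.

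**Assumptions.** Standard deviations are equal at both times and in both arms. The baseline to end-line correlation ρ is 0.3, 0.5 or 0.7. The facility intraclass correlation is 0.05 to 0.20. All are assumed.

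**Step 1: variance of the arm difference before clustering.** Relative to an end-line t-test (set to 1), a t-test on change scores has variance 2(1 − ρ), and baseline adjustment has variance 1 − ρ². The saving from adjustment is ρ² against the end-line test. Against the change score it is 1 − (1 − ρ²)/[2(1 − ρ)] = (1 − ρ)/2.

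| ρ (assumed) | End-line t-test | Change-score t-test | Baseline-adjusted | Saving against end-line | Saving against change score |
|---|---|---|---|---|---|
| 0.3 | 1.00 | 1.40 | 0.91 | 9% | 35% |
| 0.5 | 1.00 | 1.00 | 0.75 | 25% | 25% |
| 0.7 | 1.00 | 0.60 | 0.51 | 49% | 15% |

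A simulation of 20,000 trials at ρ = 0.5, with 75 workers per arm (the control number is assumed) and no clustering, gave variance ratios of 0.751 against the end-line test and 0.755 against the change score. The formula gives 0.75 for both.

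**Step 2: clustering.** Workers per facility: 75/20 = 3.75. Design effect = 1 + (3.75 − 1) × ICC:
- ICC 0.05: 1 + 2.75 × 0.05 = 1.14
- ICC 0.10: 1 + 2.75 × 0.10 = 1.28
- ICC 0.20: 1 + 2.75 × 0.20 = 1.55

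A test that ignores this reports a standard error of 1/√1.14 = 0.94 to 1/√1.55 = 0.80 of the correct one, so about 6% to 20% too small.

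**Step 3: both together at ρ = 0.5.** If the same design effect applies after adjustment, variance relative to a plain end-line t-test that ignores clustering is 0.75 × 1.14 = 0.86 at ICC 0.05 and 0.75 × 1.55 = 1.16 at ICC 0.20. The valid adjusted interval may therefore be narrower or wider than the plain one.

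**The case against.** The strongest reply is that 10.5 is a short umbrella paragraph covering surveys, assessments and interviews, and that it excludes nothing. It allows regression. The Phase 2 remark in 3.4.2, about lacking a control group for the difference between baseline and end-line, suggests that Phase 1 would compare that difference between arms. A t-test on change scores fits both sections. This stands: a reader might infer that the plan rules out use of the baseline, and the documents do not support that. They leave open how the baseline enters. A change-score test does not close the gap, however. At ρ = 0.5 it is no more precise than the end-line test, at 0.3 it is worse, and it too ignores clustering.

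The gain also depends on a correlation that the documents do not give, and on linking the same workers at both times. The plan does not say they will be linked, and it expects incoming personnel (Protocol 8.1.4). Both limits stand, so the size can only be given as a range.

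The SAP refers to a separate Phase 1 SAP that is not among the documents. It may cover these assessments, but this cannot be checked.

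Finally, competency and confidence scores are not among the primary or secondary outcomes in Protocol 7.1. That is correct and keeps the point minor.

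**Conclusion.** The point holds as a minor, inexpensive improvement. For scores planned at baseline and end-line in both arms, no baseline-adjusted comparison between arms is specified, and the tests named ignore clustering in the randomised facilities. Before clustering, the variance saving is 9% to 49% against an end-line t-test and 35% to 15% against a change-score t-test, as ρ runs from 0.3 to 0.7. These ranges rest on assumed correlations and on a baseline that can be linked to the end-line score.

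Three stronger readings are tempting and are not supported:
- A reader might infer that adjustment guarantees a narrower interval than the planned t-test. Once clustering is respected it may not, because the design effect can outweigh the saving.
- A reader might infer that the adjusted arm difference would test Hypothesis 1.3 (Protocol 2.1) as worded, which concerns e-learning modules against one-off refresher training. The arms differ in the whole package: ePOCT+, training, feedback and supervision, and added point-of-care tests. The contrast estimates the effect of that package.
- A reader might infer that the Phase 1 conclusions are in doubt. The co-primary outcomes are analysed under 10.3, which does account for clustering, and they are not affected.

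**What to change.** In Protocol 10.5, replace the between-arm t-test for competency, knowledge and confidence scores with one pre-specified model, choosing between:
- a mixed model of the end-line score on arm, baseline score, region and facility type, with a facility random intercept and a small-sample correction; or
- a facility-level ANCOVA of mean end-line score on arm and mean baseline score, which does not require individual workers to be linked.

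Name confidence scores explicitly. Report the adjusted between-arm difference with its 95% confidence interval as the effect of the intervention package on competency and confidence. Keep paired tests as description only.

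The cost is a sentence or two in 10.5 and no new data. Where staff turn over, a facility-mean baseline is a weaker covariate and the gain is smaller. The cluster-aware interval may be wider than that of a plain t-test, but it is the valid one.

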11 INFORMATION TECHNOLOGY, DATA MANAGEMENT AND MONITORING

11.1 Overall IT solution

The overall IT solution is provided by several components; some of them have been already discussed or presented previously, the diagram (**Figure 10**) below is the complete overview of the solution. From left to right we have the following components:

MedAL-Creator: The clinical algorithm management system that will allow to manage, reference, modify and deploy the different versions of the algorithm into a mobile device. MedAL-Creator is hosted in Switzerland and managed by the IT Unisanté team.

[figure not shown]
ePOCT+: The application (tablet or PC) that will contain the algorithm and be used for data acquisition by the HCW. The ePOCT+ could be deployed in a standalone or multi-device mode. In a standalone mode the application will receive updates of the algorithm directly from MedAL-Creator.

Local Data: The application that enables ePOCT+ to work in a multi-device environment. It plays a role of central database at the HF level. This software will receive the updates of the algorithm from MedAL-Creator.

Data Management System: this component will be considered as the data hub of our solution. Hosted on a server at the Dar es Salaam head office of IHI:

- MedAL-Data: This is the data collector for the country, it plays several roles:
 - o Data collector
 - o Data manager (Clean, Quality Check, Audit trail, Anonymization)
 - o Data publisher
 - o Data monitoring
- medAL-outbreak: Indicators for disease surveillance and early epidemic warning and response will be decided with and provided to CHMTs through a dedicated web-based application
- medAL-monitor: Targeted supervision to HFs by the CHMT will be organized based on the quality of care indicators calculated in real time from the uploaded data and made available through a web-based dashboard
- Research Database: This is a database only with anonymized data where the machine learning team will do their analyses.

Figure 10: IT architecture.

[figure not shown]

11.2 Data flow

The data flow is shown in **Figure 11**. Data collection starts at the HF where the study clinicians capture the data using ePOCT+. When an Internet connection is available ePOCT+ (or Local Data in multi-devices set-up) will sync the data with the data management system hosted at IHI. The data management team at IHI will monitor, clean and anonymize the data in this system and make the

anonymized data available for the Unisanté IT team. The Unisanté IT team will monitor the data received, communicate the possible errors or anomalies before sending them to the EPFL ML team for ML-based statistics.

Figure 11: Data flow.

11.3 Data security and privacy

IHI (where all the data will be stored) working with Unisanté, in collaboration with the local health management teams, will be responsible for ensuring the privacy and security of all data collected during the project, especially with respect to individual patient data. Our methods are designed to comply with international and Tanzanian human rights standards that apply to regulating patient data protection, ownership, storage and processing.

Primary data collection devices:

Tablets used for primary data collection will be password-protected and assigned to individual HFs and/or HCWs. A secure PIN will be necessary on each request to view an existing patient file. When not in use, the tablets will be locked and stored in physically secure location.

Transfer of data to secure local servers:

All data uploaded from the primary data collection devices to the local server at IHI in Tanzania will be encrypted using an SSL connection. All raw data will remain on the secure local servers in Tanzania and will not be exported as such.

Anonymization and machine learning IPD privacy:

Before being transmitted to Switzerland for machine learning analysis or the creation of reporting metrics, automated anonymization algorithms will remove identifying features of the raw data. Features removed will include names, dates of birth, addresses and identification numbers. At no point will these confidential data attributes be exported outside of the secure local server.

Transfer of data from local to Swiss servers:

When transferred from Tanzania to Unisanté in Switzerland, the data will travel through a secured VPN connection. Data Transfer Agreements (DTA) will be filled by all partners prior to any data transfer.

Additionally, machine learning analyses will explore new techniques of identifying additional feature combinations that put patient privacy at risk. We will also investigate means to export elements of the data in a manner that renders it impervious to the latest re-identification attacks, for instance, by adding carefully calibrated noise (differential privacy) or by advanced encryption. Finally, we will also explore the possibility of decentralized learning that will allow analyses to take place without data transmission.

11.4 Data quality monitoring

In order to minimize data recording errors by HCWs on the tablet, ePOCT+ data fields will include validations that limit the values to plausible ranges. Cleaning and quality assessment of the anonymized raw data arriving on the server at IHI will first be performed by the data management team using predefined algorithms developed in collaboration with the Swiss data management team. Queries related to data captured through day 7 phone calls will be brought to and solved directly with the research assistants performing the calls. Systematic missing or inconsistent data coming from HFs will be discussed first with the CHMT of the corresponding district and then with the person in-charge of the HF, if necessary. A quarterly data review meeting will be organized by the study team along with a representative of CHMTs of each district to discuss any outstanding data quality issues.

Regular quality checks will also be performed on the cleaned anonymized data sent to the Unisanté server by the Swiss team and queries sent to and solved with the IHI data management team if necessary. The database will be locked after all data has been verified and all raised queries have been resolved. Conventional and ML analyses will then start to be performed on this locked database.

11.5 Monitoring of study procedures and major health system barriers

All data related to child health or quality of the consultation, such as compliance with the algorithm by HCWs, are outcomes and indicators that will be monitored by HF teams and the CHMT using the medAL-monitor tool, and thus not directly by the study team. Indeed, it is essential that the later does not interfere with decisions taken by HCWs, persons in charge of HFs or district teams.

Regarding study procedures, monitoring will be delegated to the monitoring units of IHI and NIMR, which will function as independent monitors. In addition, the study team will perform routine on-site and off-site internal data quality and monitoring activities. The main goal of monitoring will be to assure

data quality, and the wellbeing of study participants. The study monitoring team will visit research assistants performing the day 7 phone calls once a month during Phase 1. The aim is to ensure that they attempt to reach caregivers who did not respond to the first call at least twice more, and that they do not influence caregivers in their responses regarding the child clinical outcome. The study monitoring team will visit each HF once shortly after the on-site face-to-face training to check if the intervention tools are in place and used for the purpose for which they have been designed (e.g. that informed consent is obtained correctly, or that ePOCT+ is used during the consultation and that data are not entered retrospectively after the consultation is finished) and that there are no major issues impeding basic clinical procedures (e.g. stock out of antimalarials or antibiotics for weeks). The study team will also have regular meetings with the district teams to discuss major problems related to the study, the intervention, or the tools (that may jeopardize the study) and propose solutions if any. The study team will accompany the CHMT during some of their supervision visits to monitor how they use the medAL-monitor tool and how HCW are able to perform self-auditing. A detailed monitoring plan will be developed before the start of the study.

12 ETHICAL CONSIDERATIONS

12.1 Participant information and consent

Inclusion of patients in the intervention study, as well as caregivers, HCWs, community members or CHMT members in the mixed-methods studies, will occur only if the participant has provided written informed consent. Written informed consent will be obtained prior to data collection, all non-routine clinical assessments, and any other study-related activities (except in the routine implementation of ePOCT+ in Phase 2 where the consent process will be simplified, see **Section 8.1.1**).

District and HF consent will also be obtained for the intervention. Information and consenting tasks for sick children and their caregivers may be performed by any HF staff (for more details on the informed consent procedure, see **Section 8.1.1**). Information and consenting tasks related to mixed-methods studies will be performed by the research scientists and their study team members. All these individuals will undergo adequate training with a special emphasis on the process of unbiased information of study participants ensuring that non-participation in the study does not result in a child not being adequately managed. During this training, theoretical and practical sessions will be devoted to research ethics and informed consent procedures.

The participant information sheet/informed consent documents will be available in Kiswahili. These documents, as well as their translated versions in English, are attached to the present protocol (see **Appendix 3**).

12.2 Risk-benefit assessment

Patients and caregivers:

The proposed intervention is based on international and national treatment guidelines, supplemented by POC tests that are routinely used for managing sick children at hospitals. As such, we do not anticipate that the implementation of this intervention will pose a risk to patients. We rather anticipate that the implementation of ePOCT+ will provide a direct benefit to patients by improving case management of sick children at PHC level. With reduced antibiotic prescriptions, we anticipate children to develop healthier immune systems, making them less likely to be sick in the future. Additional benefit to patients and their caregivers is the reduced cost of healthcare due to fewer reattendance visits and secondary admissions.

Community:

Communities in the intervention area are also expected to benefit from the project in several ways.

Reduced antibiotic prescriptions will reduce antimicrobial drug pressure in the community, and hence the risk of drug resistance. Better cure rates are expected to lessen the exposure to infectious diseases in the community. Enhanced disease surveillance and outbreak detection is also expected to decrease infectious disease transmission.

Health care workers:

HCWs are expected to develop better clinical skills and practices through the use of ePOCT+ and the associated training and mentorship provided through the project. The data generated with ePOCT+ will produce an opportunity for their work to also be audited by their supervisors and the CHMT. In some circumstances, this could pose some perceived or actual risk to their job security. All data available to higher managers or authorities will be de-identified to mitigate these risks as much as possible.

District health authorities:

The CHMT will be able to monitor the quality of the consultations performed by HCWs and plan better for their supervision and mentorship visits to HFs. To ensure that this insight into their daily work is not perceived by HCWs as external control but rather a support mechanism for them to improve their competencies and skills, they will have access to their own data and will be encouraged to perform self-auditing before the supervision visit by the CHMT, so that a fruitful and respectful discussion can take place during the visit. This strategy has already been shown to be very well accepted by HCWs in Burkina Faso during the implementation of a CDSA in routine conditions at primary care level (Bessat et al. 2019).

Central health system:

The cluster randomized controlled study will generate evidence about the impact of ePOCT+ under routine (versus experimental) conditions. This will support the development of guidelines for potential national scale-up of the intervention, and similar digital health tools, in the future. The economic evaluation will provide additional information on the overall costs of healthcare provision with and without the use of ePOCT+. Lower costs of medicines are anticipated, which equates to lower costs of healthcare provision at the central level because under-5 children are provided health services free of charge in Tanzania.

The project overall:

The project provides many benefits, as described above, but also comes with some risks. For example, clinicians may be hesitant to use the tool, because it is difficult to use or they feel it is too prescriptive, etc. As CDSAs cannot cover all possible clinical situations, even in a well-defined patient target group, HCWs are ultimately responsible for the clinical management of all patients and may override the recommendations of the algorithm and provide additional or withhold treatment according to their own clinical judgement. Additionally, qualitative research will be conducted to solicit user feedback and facilitate improvements to ensure that the ePOCT+ application meets user needs. Furthermore, the application may be perceived by some stakeholders as a “black box” and be wary of the use of machine learning for algorithm adaptation, which may reduce their trust in the system. To ensure full transparency, as requested more and more by stakeholders (Ansermino et al. 2019), the medical content of the algorithm used during Phase 1, as well as any modification introduced during Phase 2, even if applied only in some geographical areas or for a short period of time, will be published in real-time on the website dedicated to the DYNAMIC study. Health authorities and HCWs will thus always have access to this content and know the exact combinations of clinical predictors used to suspect or diagnose each disease. No change in the algorithm will take place automatically and all modifications will be introduced manually. ML will be used only in the background, to complement conventional statistical methods to analyze data and guide decisions of the clinical expert group. For safety reasons, ML will never be used within the algorithm. Lastly, in Phase 2 of the study, there will be no control group. There is a possibility that due to circumstances that are external to the

project (e.g. severe weather events, food insecurity, disease outbreaks) childhood morbidity and mortality could increase. In order not to incorrectly attribute poor outcomes to the study, we will need to monitor these events as closely as possible.

